#### **8.10 PREGNANCY**

This study is open to female and male subjects. Whenever possible, a pregnancy in a female subject or the female partner of a male subject exposed to IMP should be followed to term so as to assess any potential occurrence of congenital anomalies or birth defects. Any follow-up information, including premature termination and the status of the mother and child after delivery, should be reported by the investigator to the Sponsor using a pregnancy reporting/outcome form.

## **9. DATA HANDLING PROCEDURES**

### **9.1 RECORDING OF DATA**

The investigator (or delegate) will maintain individual records for each subject. These records should include dates when a subject visited the study site, study-required information and data, and other notes as appropriate. These records constitute source data.

A CRF and a subject diary will be provided by the Sponsor (or delegate) for each subject enrolled into the study. Study site staff will enter data directly into the validated electronic data capture (EDC) system by completing the CRF via a secure internet connection. The investigator is responsible for ensuring accurate and proper completion of the CRF and subject diary for recording data according to the instructions given in the CRF and subject diary.

All entries in the CRF must be backed up by the relevant source data at the study site. All source data will be kept according to all applicable regulatory requirements (Section 12.8). Source data must be completed legibly for each subject enrolled into the study and signed by the investigator (or delegate).

Data entry in the CRF and subject diary must be completed in a timely manner so that they always reflect the latest observations on the subjects enrolled in the study.

The subject's diary will be completed by the parent/caregiver at home. Data entries will be reviewed by the investigator for completion and consistency.

### **9.2 DATA QUALITY ASSURANCE**

An initiation meeting will be held before starting the study, during which the study design, procedures to be followed, and measures for ensuring standardized performance will be explained by a delegate from the Sponsor, and a common understanding of the requirements of the study will be reached with the investigator and other relevant personnel at the study site.

Data generated throughout the study will be monitored and the data entered in the CRFs will be checked against the subject records for completeness and accuracy. The Sponsor's study monitor will perform this function.

The computer system used for study data handling will be fully 21 Code of Federal Regulations (CFR) Part 11 compliant. All creation, modification or deletion of electronic study records will be documented through an automated Audit Trail. Following completion of CRF pages and entry of the data into a database, the data will be checked electronically for consistency and plausibility. Data queries will be generated for questionable data and response clarification will be sought from the investigator. These data queries must be resolved in a timely manner by the investigator (or delegate).

### **9.3 RECORD RETENTION**

A study document binder will be provided by the Sponsor for the investigator at each site for all requisite study documents (constituting the “Investigator Study File”).

Following completion of the study, the investigator will retain copies of the approved study protocol, ICF, relevant source documents, and all other supporting documentation related to the study according to applicable regulatory requirements.

The investigator is responsible for archiving the Investigator Study File, the subject’s records, and the source data according to applicable regulatory requirements. These documents have to be archived for at least 15 years or at least 2 years after the last approval of a marketing application in an ICH region, but should be retained for longer if required by regulatory requirements or by agreement with the Sponsor.

If the investigator can no longer maintain the archive of study records (eg, due to retirement or relocation), the Sponsor must be informed in writing about any change in responsibility for record retention, including the name of the new responsible party, contact information, and location of the study records. Records may not be destroyed without prior written consent from the Sponsor.

## **10. STATISTICS**

### **10.1 DETERMINATION OF SAMPLE SIZE**

The sample size will be determined by the number of subjects who participate in 1 of 3 core studies (Study ZX008-1501, Study ZX008-1502, or Study ZX008-1504) and who volunteer for the extension study and meet the necessary criteria for enrollment. Approximately 100-120 subjects are expected to participate in each of the core studies; thus, if all participants also enroll in the extension, the total sample size of the extension study would be approximately 340.

### **10.2 ANALYSIS POPULATIONS**

#### **10.2.1 Safety (SAF) Population**

Safety analyses will be performed on the Safety (SAF) Population defined as all subjects who receive at least one dose of ZX008 during the open label extension.

#### **10.2.2 Modified Intent-to-Treat (mITT) Population**

The modified Intent-to-Treat (mITT) Population is defined as all subjects who receive at least one dose of ZX008 and have valid seizure data during the open label extension. Effectiveness analyses, such as evaluating the change in the frequency of convulsive seizures, will be performed on the mITT Population.

#### **10.2.3 Per Protocol (PP) Population**

The Per Protocol (PP) Population is defined as all subjects who receive at least one dose of ZX008, complete the entire OLE Treatment Period of the open label extension, and have no major protocol deviations that would have a significant impact on clinical outcome. Key effectiveness analyses will be repeated on the PP Population in addition to the mITT Population.

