## 1. INTRODUCTION

### 1.1 BACKGROUND INFORMATION ON INDICATION STUDIED

ZX008 (fenfluramine hydrochloride) is under clinical development for the adjunctive treatment of patients with Dravet syndrome (DS) and Lennox-Gastaut syndrome. Fenfluramine (Fintepla®) is authorized for sale in the United States for the treatment of seizures associated with Dravet syndrome in patients 2 years of age and older

Dravet syndrome, previously known as severe myoclonic epilepsy of infancy (SMEI), is a rare and severe form of epilepsy first described by Charlotte Dravet in 1978 (Dravet 1978). The International League Against Epilepsy (ILAE) considers Dravet syndrome a developmental and epileptic encephalopathy, “a condition in which the epileptic activity itself may directly contribute additional cognitive and behavioral impairments over those expected from the underlying etiology alone and that suppression of epileptic activity might minimize this additional impairment” (Scheffer 2017).

Dravet syndrome is estimated to affect 1 out of every 15,700 live births in the US and less than 1 in 20,000 persons in the European Union (Wu 2015; EMA 2014). Dravet syndrome is responsible for 7% of the severe epilepsies starting before the age of 3 years (Ceulemans 2004).

The diagnosis of Dravet syndrome is based on clinical signs and symptoms, though the presence of a mutation in the SCN1A gene is considered a likely, though not definitive, marker for the disorder (Dravet 2011; Fujiwara 2006). Dravet syndrome is usually not diagnosed until at least 1 year of age (Cooper 2016) and is characterized by medically intractable seizures along with motor and neurodevelopmental comorbidities. Onset of the first seizure typically occurs in the first year of life (usually at 5 to 8 months of age) in otherwise healthy infants and most often consists of prolonged, unilateral or generalized, clonic seizures provoked by fever (Orphanet 2014; Ceulemans 2004; Dravet 2011). These patients will have poor response or worsening seizures to standard antiepileptic drugs, in particular, sodium channel antagonist medications (Dravet 2011).

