### 3. INVESTIGATIONAL PLAN

#### 3.1 OVERALL STUDY DESIGN AND PLAN

This is an international, multicenter, open-label, long-term safety study of ZX008 in pediatric and young adult subjects with DS. Subjects eligible for participation are those who have successfully completed 14 weeks of treatment in core studies ZX008-1501 or ZX008-1502, and 15 weeks of treatment in core study ZX008-1504 Cohort 2, or successfully completed core study ZX008-1504 Cohort 1, and are candidates for continuous treatment for an extended period of time. In addition, subjects who are >18 to ≤35 years of age at the time of screening, and who meet all other eligibility criteria may be eligible for participation after discussion with the Medical Monitor and sponsor about the potential risks and benefits for receiving ZX008. Participation for these subjects will be at the discretion of the sponsor.

This trial will consist of an up to 36-month open-label extension (OLE) Treatment Period and a 2-week Post-Dosing Period. Thus, subjects who complete this trial will have been treated with ZX008 for a minimum of up to 3 years (including their participation in both the core study and this study). Subjects who did not participate in one of the core studies will undergo a screening period up to 28 days to confirm eligibility prior to receiving their first dose in the OLE Treatment Period

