After at least 1 year of treatment in Study 1503 subjects who participated in one of the core studies will transition to a separate extension study (Study 1900) once that study is approved and the study site is initiated. Continuation in a separate extension protocol will be based on benefit/risk and continued eligibility criteria being met. De novo subjects must have participated in this trial for at least 3 months with at least 1 ECHO completed and continue to meet eligibility requirements to be eligible to transition to a separate extension protocol. Alternatively, subjects will transition to commercial product once it is available. For subjects who are entering the separate extension trial or who transition to commercially available drug, post-dosing and cardiac safety follow-up visits are not required in this trial. Subjects who transition to commercially available drug must have an ECHO within 3-6 months before starting commercial drug and will have follow-up ECHOs within the required timeframe while on commercial drug.

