### **3.3 STUDY DURATION**

The duration of participation in the study for an individual subject is expected to be up to 158 weeks, plus follow-up safety visit 3 and 6 months after the last dose:

- OLE Treatment Period - 36 months (156 weeks)
- Post-Dosing Visit - 2 weeks after study completion or early termination
- Cardiac Follow-up (ECG and ECHO) - 3 and 6 months after study drug discontinuation for early termination and for those subjects who complete the study; not applicable to subjects who transition to commercial product.

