### **6.1.5 Clinic Visit 16 (Month 36): End of Study/Early Termination**

The End-of-Study participation for an individual subject occurs after he/she has received IMP for 3 years in the OLE Treatment Period or if the subject is transitioning to receive ZX008 in a separate extension protocol when available or until ZX008 is approved in a subject's country of residence and listed on a patient's health plan formulary, whichever occurs first.. The End-of-Study visit may also occur if the subject withdraws participation from the study or the Sponsor terminates the study.

Subjects will visit the clinic for the End-of-Study visit if one the following events occur:

1. The subject withdraws or is withdrawn from participation in the study.
2. The Sponsor terminates the study.
3. The subject completes all study related visits and procedures.
4. The subject is being transitioned to another extension study or transitioning to commercially available drug.

The following procedures will be performed:

- Review current seizure activity (number/type/duration) from diary since previous visit
- Record concomitant medications
- Complete physical examination, including height and weight, and calculation of BMI
- Complete neurological examination
- Obtain vital signs
- 12-lead ECG
- Doppler ECHO (must be performed any time between Study Day 1064 and Study Day 1085; if subject terminates early from the study, the ECHO should be scheduled as soon as practical). If the Month 3, 6, 9, 12, 15, 18, 21, 24, 27, 30, or 33 ECHO was completed  $\leq$  30 days prior to early termination, the Visit 12 ECHO will not be performed provided the parent/guardian agrees to bring the subject to the clinic for the cardiac follow-up visit (Table 8).
- Urine pregnancy test for females of child-bearing potential

- Laboratory evaluation (serum chemistry and hematology, and urinalysis)
- Urine THC panel
- Whole blood CBD
- Collect plasma sample for AED PK evaluation prior to the morning dose of study medication(s)
- Tanner Staging for subjects > 7 to ≤18 years of age ([Appendix 5](#))
- Collect and review diary with parent/caregiver
- C-SSRS Children's Since Last Visit Assessment ([Appendix 2](#))
- CGI-I (assessed by parent/caregiver)
- CGI-I (assessed by investigator)
- BRIEF ([Appendix 3](#))
- QOLCE ([Appendix 4](#))
- PedsQL ([Appendix 6](#)) (only for subjects from the core studies)
- Parent/Caregiver QoL using the EQ-5D-5L scale ([Appendix 7](#))

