#### Open-Label Extension Treatment Period

The OLE Treatment Period covers the 36 months during which subjects will receive open label treatment with ZX008.

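### The Per Protocol definition requires the full 36-month treatment period, while the same protocol directs compliant subjects to leave earlier

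*Protocol*

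**What the plan says.** Section 10.2.3 limits PP to subjects who take at least one dose and "complete the entire OLE Treatment Period of the open label extension, and have no major protocol deviations" of a kind that would significantly affect clinical outcome. The key effectiveness analyses are then repeated on PP in addition to mITT.

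Section 10.4 gives the length without qualification: "The OLE Treatment Period covers the 36 months during which subjects will receive open label treatment with ZX008". Section 3.3 does the same: "OLE Treatment Period - 36 months (156 weeks"). Section 3.1 treats it as a maximum: "This trial will consist of an up to 36-month open-label extension (OLE) Treatment Period".

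Section 3.1, repeated in Section 10.4 under the post-dosing period, says that after at least 1 year "subjects who participated in one of the core studies will transition to a separate extension study (Study 1900"), once that study is approved and the site is initiated. Continuation there depends on benefit/risk and eligibility. The alternative is a move to commercial product once it is available, for which no minimum time on study is given.

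Section 6.1.5 ends participation at 3 years of treatment, at transfer to another extension protocol, or when the product is approved in the subject's country and "listed on a patient's health plan formulary, whichever occurs first".

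**The concern.** Leaving for Study 1900 or for commercial drug is something the protocol instructs, not a deviation from it. Yet a subject who does so before Month 36 has not completed 36 months and, on the plain wording, is outside PP. Membership then turns on when Study 1900 opened at the site and on local approval and formulary listing.

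A per-protocol repeat is meant to show whether the mITT result holds among subjects who adhered. If the two results differed here, the reader could not tell whether adherence, length of follow-up, or site and country mix was responsible. The exclusion also gains little: the convulsive-seizure objective in Section 2.2 covers Year 1 (Day 31 to 365 and Day 1 to 365), so a subject who transfers at Month 15 with complete Year 1 data has already supplied what that objective needs.

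**Working it through.** **The plan's own figures.** 36 months = 36 × 365.25 / 12 / 7 = 156.5 weeks, against the 156 stated in Section 3.3. Adding the 2-week post-dosing period gives 156 + 2 = 158 weeks, as stated. Section 10.1 expects 100 to 120 subjects in each of three core studies, so 300 to 360, consistent with its figure of approximately 340.

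**The rules side by side.**

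| Rule | Section | Requirement |
|---|---|---|
| PP completion | 10.2.3 | the entire treatment period |
| Length of that period | 10.4, 3.3 | 36 months |
| Length of that period | 3.1 | up to 36 months |
| Transfer of core-study subjects to Study 1900 | 3.1, 10.4 | after at least 1 year, conditional |
| Transfer to commercial product | 3.1, 10.4 | when available, no minimum time |
| End of participation | 6.1.5 | 3 years, transfer, or approval with formulary listing, whichever is first |

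The earliest transfer to Study 1900 falls about Day 365 of a schedule that ends on Day 1085: 365 / 1085 = 34% of the period.

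**Size of PP on the 36-month reading.** PP = N × (1 − t) × (1 − d), where
- N = 340, from Section 10.1. This is an upper bound on the planned base for change-from-baseline analyses: it includes ZX008-1504 Cohort 1, which Section 10.5.2.1 excludes. De novo subjects come on top of the 340, and the synopsis excludes them from effectiveness analyses.
- t = share transferring before Month 36. The protocol gives none; assumed 10% to 90%.
- d = loss for other reasons (dropout, major deviation). The protocol gives none; assumed 0% to 20%.

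| t | PP, d = 0% | PP, d = 20% |
|---|---|---|
| 10% | 306 | 245 |
| 25% | 255 | 204 |
| 50% | 170 | 136 |
| 75% | 85 | 68 |
| 90% | 34 | 27 |

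Example: 340 × (1 − 0.50) × (1 − 0.20) = 136.

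**With completion tied to Day 365.** Transfers after Visit 8 no longer count against PP. If nobody leaves for commercial drug before Day 365, t = 0 and PP = 340 × (1 − d), which is 272 at d = 20% and 340 at d = 0%. Earlier moves to commercial drug would reduce this.

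**The case against.** The strongest reply is that a transferring subject can be read as a completer. Section 3.1 calls the period up to 36 months, Section 6.1.5 makes transfer an End-of-Study event, and Section 6.2 does not simply equate transfer with early discontinuation. This softens the conflict but does not remove it. Section 10.2.3 says entire, Section 10.4 has no up to, and Section 6.1.5 lists completing all visits and procedures separately from being transitioned. No section states which reading governs PP.

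A second reply is that operational rules belong in the SAP. That covers how a major deviation is judged, but the protocol itself fixes the completion requirement and the transfer rule.

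Third, the stakes are modest. The primary objective is safety, analysed on the Safety population. Effectiveness is analysed on mITT, and PP only repeats it. This stands, and it limits the weight of the point.

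Several stronger inferences are tempting but unsupported:
- That subjects leave at about 1 year. One year is a conditional floor, not a timetable.
- That US authorisation empties the study. Section 1.1 says the product "is authorized for sale in the United States for the treatment of seizures associated with Dravet syndrome", but Section 6.1.5 looks to approval in the subject's own country together with formulary listing.
- That PP necessarily over-represents responders. Section 4.4 allows discontinuation for worsening seizures, which pushes that way, but entry to Study 1900 itself depends on benefit/risk, so the net direction is undetermined.
- That the de novo 3-month rule shrinks PP. De novo subjects are already outside the effectiveness analyses.

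**Conclusion.** The defect holds: as written, Section 10.2.3 can exclude fully compliant subjects for reasons unrelated to adherence. Its size is unknown. On an upper-bound base of 340, PP ranges from 306 (10% transferring) to 34 (90% transferring) before other losses, and both transfer shares are assumptions.

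A reader might infer that PP will be a small remnant. The documents do not establish that. They give no transfer share, and half transferring would still leave 136 to 170 subjects. Section 1.3 reports Month 24 as the longest duration in the October 2019 update, while Section 1.10 speaks of participation of up to 3 years, so some early entrants may have reached or approached Month 36. Nor does it follow that PP would carry no information on adherence, since it also removes major deviations.

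This should be corrected because the change is cheap, but it does not threaten the primary safety objective or the mITT results.

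**What to change.** In Section 10.2.3, replace the completion requirement with completion of Visit 8 (Day 365) and no major protocol deviation up to then. State that protocol-directed transfer after Visit 8 does not forfeit PP. Run the PP repeat and its mITT comparison on the same Year 1 window, matching the objective in Section 2.2, and align Sections 3.1, 6.1.5, 10.4 and 10.5.2.1. Section 10.5.2.1 needs attention because it defines the key endpoint over the whole treatment period.

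Counting every protocol-directed transfer as completion would be simpler, but the commercial route has no minimum time on study, so it could admit subjects with very short exposure.

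The cost is a few sentences in the protocol and matching SAP text, with no new data. It should be settled before database lock, because choosing a reading afterwards could be influenced by the results. There are two small downsides: subjects who move to commercial drug before Day 365 remain outside PP, and the PP repeat no longer covers the full treatment period.

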### **10.3 TREATMENT GROUPS**

All subjects will receive ZX008 and will be considered a single treatment group.

### **10.4 TREATMENT PERIODS**

#### **Pre-ZX008 Baseline Period**

For subjects who receive ZX008 in Study ZX008-1501, Study ZX008-1502, or Study ZX008-1504 Cohort 2, the pre-ZX008 baseline period is equivalent to the core study pre-

randomization baseline period, ie, the approximately 42-day span just prior to randomization and start of treatment in the core study.

For subjects who receive placebo in Study ZX008-1501, Study ZX008-1502, or Study ZX008-1504 Cohort 2, the pre-ZX008 baseline period begins with the core study pre-randomization baseline period and extends through the entire span of the core study up to the transition period. The pre-ZX008 baseline period for a subject ends when that subject receives their first treatment with ZX008.

Study ZX008-1504 Cohort 1 have a shortened (exploratory) baseline period of approximately 12 days (after the single-dose PK assessment) and this will be used in an exploratory manner.

For de novo subjects, the pre-ZX008 baseline period is the screening period of up to 28 days prior to receiving the first dose.

The baseline frequency of convulsive seizures will be calculated from data collected during the entire length of the pre-ZX008 baseline period.

#### Open-Label Extension Treatment Period

The OLE Treatment Period covers the 36 months during which subjects will receive open label treatment with ZX008.

#### Post-dosing Period

The Post-dosing Period begins immediately at the end of OLE Treatment Period and extends for 2 weeks.

After at least 1 year of treatment in Study 1503 subjects who participated in one of the core studies will transition to a separate extension study (Study 1900) once that study is approved and the study site is initiated. Continuation in a separate extension protocol will be based on benefit/risk and continued eligibility criteria being met. De novo subjects must have participated in this trial for at least 3 months with at least 1 ECHO completed and continue to meet eligibility requirements to be eligible to transition to a separate extension protocol. Alternatively, subjects will transition to commercial product once it is available if they have had an ECHO within 3-6 months before starting commercial drug. For subjects who are entering the separate extension trial or who transition to commercially available drug, post-dosing and cardiac safety follow-up visits are not required in this trial. Subjects who transition to commercially available drug will have follow-up ECHOs within the required timeframe while on commercial drug.

